4.5. Timing of outcome assessments

The schedule of trial procedures and outcome assessments are given in Appendix C.

4.6. Randomisation

Participants will be randomised online via a secure internet facility at the level of the individual in a 1:1 ratio to either letrozole or clomifene and at the same time randomised to metformin or placebo.

A minimisation algorithm will be used within the online randomisation system to ensure balance in the treatment allocations (both randomisations will occur simultaneously, effectively resulting in four allocation groups) over the following variables:

- maternal age (<35 and ≥35 years);
- body mass index (<30 and \geq 30 kg/m²);
- any previous pregnancy (yes and no);
- previous exposure to either clomifene or letrozole;
- any menstrual periods in the preceding 6 months (yes and no);
- randomising centre

A 'random element' will be included in the minimisation algorithm, so that each participant has

a probability (unspecified here) of being randomised to the opposite treatment that they would have otherwise received.

Full details of the randomisation specification will be stored in a confidential document at BCTU.

4.7. Sample size

Original sample size

Just under two thousand participants (n = 1,992) will provide greater than 99% power (at p=0.05) to detect differences in the letrozole vs clomifene comparison (assuming rates of 39% vs 29% respectively for rate of live birth \geq 34 weeks) and the same power to detect differences in the metformin vs placebo comparison (also assuming rates of 39% vs 29%, respectively). Adjusting for a worst-case scenario of 5% attrition, the total number required will be 2,100 participants. The high rate of power (>99%) has been chosen to ensure we will have 90% power (p=0.05 and 1,050 participants) to answer the further question of letrozole plus metformin vs clomifene plus metformin (the latter comparison assuming rates of 44% and 34%, respectively).

The basis for the proportions used in these calculations is provided in the next paragraph.

The live birth rates used in the sample size calculations were taken from our systematic review (see protocol Table 8). We used the estimate in the clomifene alone group (24%) as the base estimate for these calculations as this was by far the largest group, involving 36 trial groups and 2,299 women; it was also the most conservative estimate (lowest rate), which was important as information was only available on the rate of pregnancy and not live birth rate. A 10% absolute increase was identified in our clinician survey as minimally important, so we chose this as the difference we wanted to detect when comparing clomifene with letrozole or with the addition of metformin (i.e., both increased to 34%). We assumed using both letrozole and metformin would have an additive effect, i.e. increased to 44%. Overall, this amounted to an assumption of 29% versus 39% in the two main comparisons (letrozole vs clomifene and metformin vs placebo) when we take into account the factorial design (i.e. the overall rates at the margins). No interaction of the effect is assumed in these calculations as the biological mechanism of these agents is considered sufficiently different and, to our knowledge, is unlikely to have a pronounced effect on outcome.

Revised sample size

Following review by the funder (NIHR HTA) and due to the impact of the COVID-19 pandemic on participant accrual, the sample size target was revised on 3 February 2023 to aim for at least 80% power within the letrozole plus metformin vs clomifene plus metformin comparison, rather than the 90% power originally described. 800 participants (with primary outcome data gained on 760) within this comparison would provide 81% power (p=0.05) to detect a difference of 10% between groups (the same assumptions of 44% and 34% in the two groups as previously stated).

Due to the factorial design, this agreement would mean a sample of 1600 participants (with primary outcome data gained on 1520 assuming 5% loss to follow-up) within the two main comparisons (letrozole vs clomifene and metformin vs placebo). This number of participants would provide 98.5% power (at p=0.05) to detect a difference of 10% between groups (the same assumption of 39% vs 29% in both comparisons as previously stated).

4.8. Framework

The objective of the trial is to test the superiority of one intervention to another in the three trial comparisons (see section 4.12 for list of these comparisons).

The null hypothesis is that there is no difference in the proportion of women randomised who experience a live birth at and beyond 34 weeks of gestation between the intervention groups. The alternative hypothesis is that there is a difference between the groups.

4.9. Interim analyses and stopping guidance

A separate Data Monitoring Committee (DMC) reporting template was drafted and agreed by the DMC including an agreement on which outcomes were to be reported at interim analyses. The statistical methods stated in this SAP was followed for the outcomes included in the DMC report, where possible.

Interim presentation of safety and efficacy data to the independent DMC took place during the study. The committee met prior to study commencement to agree the manner and timing of such analyses including the analysis of the primary and major secondary outcomes and full assessment of safety (SAEs) at least at annual intervals. Criteria for stopping or modifying the study based on this information was ratified by the DMC and therefore no formal stopping rules were applied.

4.10. Timing of final analysis

The final analysis for the study will occur once all participants have completed all assessments and corresponding outcome data has been entered onto the study database and validated as being ready for analysis.

This is provided that the trial has not been stopped early for any reason (e.g. DMC advice or funding body request).

4.11. Timing of other analyses

Not applicable.

4.12. Trial comparisons

The three primary comparisons will be composed of:

- A) those randomised to letrozole versus those randomised to clomifene;
- B) those randomised to metformin versus those randomised to placebo; and
- C) those randomised to letrozole plus metformin versus those randomised to clomifene plus metformin.

Analyses will be conducted separately for each comparison. Unless stated otherwise, the methods detailed here will be applicable to each comparison.

In addition, there will be a further two exploratory comparisons:

- D) letrozole plus metformin versus letrozole
- E) clomifene plus metformin versus clomifene

The five comparisons are considered distinct questions and will be reported separately; hence no adjustment for multiple testing across comparisons is proposed.

5. Statistical Principles

5.1. Confidence intervals and p-values

For all primary and secondary outcomes, estimates of differences between groups will be presented with measures of uncertainty (95% confidence intervals), unless otherwise stated. For the primary outcome, a p-value will be produced, with statistical significance considered at the 5% level. A 95% confidence interval will be utilised. P-values will be presented for the safety outcomes (see section 5.2).

5.2. Adjustments for multiplicity

As detailed in section 4.12, the trial will have three main separate comparisons plus two exploratory comparisons. These comparisons are considered distinct questions and will be reported separately. Therefore, no adjustments for multiple testing are proposed from this perspective.

Safety outcomes will be subject to statistical testing without adjustment for multiple testing as adjustment for multiplicity is counterproductive for considerations of safety¹.

5.3. Analysis populations

Participants will be analysed in the treatment group to which they were randomised, regardless of treatment compliance. Analysis populations will be as follows:

- Primary outcome, live birth at or beyond 34 weeks: all randomised participants. Analyses will also be produced using women who achieved pregnancy, defined as a positive pregnancy test (urine or serum beta-hCG test >10 mIU/ml), as the denominator but this will be treated as supportive evidence only)
- Secondary outcomes:
 - (Treatment outcomes) Ovulation rate, time from randomisation to pregnancy: all randomised participants
 - (Treatment outcomes) Number of ovulation induction cycles required for pregnancy: women who achieved pregnancy (defined as a positive pregnancy test (urine or serum beta-hCG test >10 mIU/ml))
 - (Pregnancy end outcomes) Ongoing pregnancy at 12 weeks (range 11⁺⁰ to 14⁺⁰ weeks) of gestation, pregnancy loss (defined as pregnancy loss <24 weeks of gestation), termination, stillbirth, molar pregnancy, pregnancy of unknown location, ectopic pregnancy, multiple live births: all randomised participants (analyses will also be produced using women who achieved pregnancy, defined as a positive urine or serum beta-hCG test >10 mIU/ml, as the denominator but this will be treated as supportive evidence only)
 - Time from conception to delivery (gestational age at live birth), gestational age <28/<32/<37 weeks, singleton live births at and beyond 34 completed weeks of gestation, live births at and beyond 37 completed weeks of gestation, mode of birth (unassisted vaginal, instrumental vaginal, elective caesarean section, emergency caesarean section, vaginal breech birth, other), number of ovulation induction cycles to live birth ≥24 weeks : women with live birth ≥24 weeks
 - Birth weight, APGAR score (at 1, 5 and 10 minutes) and APGAR score <7 out of 10 (at 1, 5 and 10 minutes): babies born alive ≥24 weeks
 - Antenatal outcomes: women achieving pregnancy
 - o Intrapartum outcomes: women with live birth≥24 weeks
 - Post-partum outcomes: women with live birth≥24 weeks
 - Maternal outcomes: all randomised participants

- Neonatal outcomes: babies born alive ≥24 weeks.
- Survival at 28 days of neonatal life: babies born alive ≥24 weeks
- Safety outcomes:
 - \circ Neonatal congenital or chromosomal abnormalities: babies born alive ≥24 weeks
 - Maternal adverse events (tabulated but not formally analysed), multiple pregnancies, ovarian hyperstimulation syndrome (OHSS), serious adverse events (SAEs): all randomised participants
 - Side effects attributed to clomifene/letrozole and metformin/placebo: all randomised participants

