# 8.1.3. Secondary Outcomes

# 8.1.3.1. Key secondary outcomes

- 1. Pregnancy loss (defined as pregnancy loss before 24 weeks of gestation)
- 2. Number of ovulation induction cycles to live birth

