9.6. Analysis methods – secondary outcomes

A template for reporting the secondary outcomes will be given in a separate template report. See section 9.1 for covariate adjustment and model convergence.

Dichotomous outcomes (e.g. pregnancy loss and APGAR score <7) will be analysed using the same regression approach as the primary outcome, using the denominators detailed in section 5.3. Pregnancy events will be limited to those who conceived during the six ovulation induction cycles (maximum 240 days). For pregnancy end outcomes, in the event of babies from a multiple pregnancy having different outcomes, for example one live birth and one miscarriage, both the events will be counted in the separate categories (i.e. they will contribute to both a live birth event and a miscarriage event.

Mixed-effects Poisson regression will be used for count data (number of ovulation induction cycles to live birth) with an Incidence Rate Ratio (IRR) and confidence interval generated (if there is evidence of overdispersion then a negative-binomial model will be fitted instead). This outcome will be reported as count data (i.e. 1, 2, 3, 4, 5, and 6).

For continuous secondary outcome measures (e.g. birthweight and gestational age) means and standard deviations will be reported alongside adjusted mean differences (with confidence intervals) estimated using a mixed effects linear regression model.

A Cox Proportional Hazard (PH) model (provided the assumptions of proportionality are met) will be utilised for time to event data (time from randomisation to pregnancy). Data will be summarised with medians and interquartile ranges and estimates of difference presented as adjusted hazard ratios (with confidence intervals). A Kaplan Meier plot will be produced to assess the data visually. In this model, randomising centre will be regarded as a shared frailty.

Mode of birth will be analysed as unassisted vaginal versus any other category; all categories of data will be presented.

For birthweight, babies from multiple births will be included as separate babies. To allow for the clustering at the mother level a robust variance estimator clustered by mother will be included in the model. If this does not work (e.g. failure to converge) then analysis on the mother's level will be used instead and the outcome interpreted as such.

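### Singleton live birth ≥34 weeks, live birth ≥37 weeks and cycles to live birth are analysed only in women who delivered, so their estimates are not effects per woman randomised

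*SAP*

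**What the plan says.** SAP 5.3 lists several outcomes in one bullet with one population, women with a live birth at 24 weeks or later. The bullet includes "singleton live births at and beyond 34 completed weeks of gestation, live births at and beyond 37 completed weeks of gestation" and ends with "number of ovulation induction cycles to live birth ≥24 weeks : women with live birth ≥24 weeks".

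SAP 9.6 analyses dichotomous secondary outcomes "using the denominators detailed in section 5.3". For cycles it says "Mixed-effects Poisson regression will be used for count data (number of ovulation induction cycles to live birth"), and "This outcome will be reported as count data (i.e. 1, 2, 3, 4, 5, and 6"). A woman without a live birth has no value on that scale and drops out of the analysis.

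SAP 5.1 asks for between-group estimates with 95% confidence intervals for all primary and secondary outcomes. SAP 9.10 limits sensitivity analyses to the primary outcome, so no all-randomised version of these three outcomes is planned.

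Pregnancy end outcomes in SAP 5.3 are handled the other way round. The entry for the last of them reads "multiple live births: all randomised participants (analyses will also be produced using women who achieved pregnancy", and the version restricted to pregnant women is supportive only. The primary outcome follows the same pattern.

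Protocol 8.1.3.1 lists "Number of ovulation induction cycles to live birth" as a key secondary outcome, with no restriction to women who delivered. Protocol 8.1.3.2 and SAP 4.4 place the two binary outcomes under a heading limited to live births at 24 weeks or later. SAP 4.4 places cycles to live birth under treatment outcomes.

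**The concern.** Having a live birth happens after randomisation, and it is what the treatments are meant to change. Once the analysis is limited to women who had one, the groups compared are no longer the randomised groups. A drug that produces more live births adds women to the numerator and the denominator together, so its benefit largely cancels.

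For cycles, the women left out are those in whom up to six cycles led to no live birth. The mean among successes reflects how successes are spread over cycles 1 to 6, not how many there are.

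At stake are estimates and intervals that will be printed beside the primary result and read as treatment effects. Two of these outcomes are stricter forms of the primary outcome, which makes that reading natural.

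**Working it through.** **Inputs from SAP 4.7 (revised sample size).** Live birth ≥34 weeks 39% vs 29%; 1,520 women analysed in each main comparison, so 760 per arm.

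**The plan's own figure.** Two-sided 5% test of two proportions, pooled variance, 760 per arm, 39% vs 29%: power 98.5%, as stated. For letrozole plus metformin vs clomifene plus metformin, 380 per arm, 44% vs 34%: 80.8%, stated as 81%.

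**Cycles to live birth, constant per-cycle success (assumption).** The ≥34-week rates stand in for live birth ≥24 weeks.

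- Per-cycle probability h = 1 − (1 − P)^(1/6): 1 − 0.61^(1/6) = 0.0791 and 1 − 0.71^(1/6) = 0.0555.
- Probability of success at cycle k is h(1 − h)^(k−1). The mean of k among successes over k = 1 to 6 is 3.26 vs 3.33.
- Incidence rate ratio (IRR) = 3.261/3.334 = 0.978.
- Women contributing: 760 × 0.39 = 296 and 760 × 0.29 = 220.
- Poisson SE of log IRR = √[1/(296.4 × 3.261) + 1/(220.4 × 3.334)] = 0.049.
- 95% CI = exp(−0.0222 ± 1.96 × 0.049) = 0.89 to 1.08.
- The same rates in all randomised women, on the complementary log-log scale, give a hazard ratio of ln(0.61)/ln(0.71) = 1.44.

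If instead 95% of live births ≥24 weeks reach 34 weeks (assumption), the rates become 41.1% vs 30.5%, the means 3.24 vs 3.32, and the IRR is still 0.98.

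**Other hazard paths (illustrations, linear over cycles 1 to 6).**

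| Path | Per-cycle success | Overall | Mean cycles | IRR |
|---|---|---|---|---|
| Early advantage | 0.11 falling to 0.05 vs constant 0.0555 | 39.5% vs 29.0% | 2.81 vs 3.33 | 0.84 |
| Constant | 0.0791 vs 0.0555 | 39.0% vs 29.0% | 3.26 vs 3.33 | 0.98 |
| Late advantage | 0.06 rising to 0.09 vs 0.06 falling to 0.045 | 37.4% vs 27.7% | 3.52 vs 3.17 | 1.11 |

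Each row has a benefit of about 10 points, yet the IRR falls on either side of 1.

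**Singleton ≥34 weeks and live birth ≥37 weeks.** Assume that 95% of live births ≥24 weeks reach 34 weeks, and that a share s of live births ≥24 weeks, equal in both arms, meets the stricter outcome. Neither figure is in the documents.

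- Live birth ≥24 weeks: 0.39/0.95 = 41.1% and 0.29/0.95 = 30.5%, or 312 vs 232 women.
- SAP denominator: s vs s, so the relative risk (RR) is 1.00 and the difference 0.
- All randomised, s = 0.80: 32.8% vs 24.4%, difference 8.4 points.
- All randomised, s = 0.95: 39.0% vs 29.0%, difference 10.0 points.
- The all-randomised RR is 0.39/0.29 = 1.34 at any common s.

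Unequal shares can split the two readings. With 88% vs 92%, the conditional RR is 0.88/0.92 = 0.96, while the all-randomised RR is (0.411 × 0.88)/(0.305 × 0.92) = 1.29.

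**The case against.** The strongest defence is that these are legitimate descriptions of women who delivered. Both documents put the two binary outcomes under a live-birth heading, so for them SAP 5.3 follows the protocol. That stands: the conditional results are informative about multiplicity, prematurity and cycles used among successes, and should be kept. A reader might infer that they show nothing useful. The documents do not support that; what they fail to estimate is the effect per woman randomised.

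A reader might also infer that the plan never measures benefit or multiplicity per woman randomised. It does in part. The primary outcome, multiple live births, multiple pregnancies and time from randomisation to pregnancy all use all randomised women. Missing on that denominator are singleton live birth ≥34 weeks, live birth ≥37 weeks and a cycle-based live-birth analysis.

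A third tempting reading is that the cycles analysis lacks power or points the wrong way. SAP 5.1 plans p-values for the primary and safety outcomes, not for these, so power describes a test that the SAP does not plan. The direction depends on how any advantage is spread over cycles, which the documents do not state: an early advantage gives an IRR well below 1, and reversal needs a late one.

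Finally, the key-secondary label for cycles comes from protocol v1.0. The SAP has no key tier, so the label does not by itself make the point more serious.

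**Conclusion.** The point holds in this form. SAP 5.3 conditions three outcomes on a success that treatment is expected to change, and SAP 5.1 still asks for between-group estimates and intervals. Those results describe women who delivered and should not be read as efficacy.

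Under the assumptions shown, a 10-point benefit appears as an IRR of about 0.98 for cycles, or anywhere from about 0.84 to 1.11 on the other paths tried. For the two binary outcomes it appears as an RR of 1.00 where the per-randomised RR is about 1.34. The hazard paths, the equal shares and the 95% figure are assumptions; that the denominator depends on treatment is not.

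The primary conclusion is untouched, and no formal claim rests on these outcomes under the SAP. The risk is misinterpretation of secondary results, and it is worth correcting because the correction is cheap.

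**What to change.** 1. In SAP 5.3, make all randomised women the main denominator for singleton live birth ≥34 weeks and live birth ≥37 weeks. Keep the live-birth denominator as supportive, as the SAP already does with the pregnancy denominator for pregnancy end outcomes.
2. Label the 1 to 6 cycle count among women with a live birth as descriptive.
3. Add the cumulative incidence, by cycle 1 to 6 within 240 days, of conception leading to live birth in all randomised women, with a discrete-time model for the comparison.
4. State the risk set. Women who stop early, or who lose a pregnancy without a later live birth, stay in as non-events through cycle 6. Only women whose outcome is unknown through withdrawal or loss to follow-up are censored. Censoring every woman after her last cycle would treat stopping as uninformative. That is doubtful: Protocol 1.2.2 cites a trial in which 16% vs 5% discontinued because of gastrointestinal effects of metformin.

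The cost is SAP wording and a little more analysis. The data are already on forms 03, 04 and 07.

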5.4. Definition of adherence

Adherence will be monitored by tablet counting in the first instance with the participants' honest assessment of their drug compliance if tablet counting is not possible (recorded as a percentage). For clomifene/letrozole, this will be reported for the OI phase; for metformin/placebo, this will be reported separately for the OI phase and for the pregnancy phase (participants will need to be adherent in both phases to be considered adherent overall in any analysis).

We will define and summarise adherence in the following categories: number that received \geq 75% randomised allocation; number that received <75% randomised allocation; unknown compliance information.

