# 7. TRIAL TREATMENT / INTERVENTION

# 7.1. Patient pathway

Randomisation into the trial will be considered the first visit (Visit 1) in the trial. Subsequent visits will depend on whether the participant has become pregnant. At this first visit, baseline medical details will be collected by staff prior to ovulation induction (OI) lasting up to six months. Participants will also be given a treatment diary to complete during the trial.

Should pregnancy be confirmed, participants will be advised to contact the trial team and arrange for Visit 2. At six months, if the participant has not contacted the research team, a member of the site team will call the participant to determine whether they have become pregnant. If a pregnancy is confirmed, Visit 2 may be booked at this point. Visit 2 is only for participants who have become pregnant. They will be asked to return any unused OI drugs and collect additional Metformin/placebo supply to last until 14 weeks gestation.

For participants who have not become pregnant by the end of the six months, the compliance assessment and end of study forms should be completed. Participants may return unused drugs at their next routine fertility clinic appointment.

Please see Figure 7 for an illustration of the participant pathway.

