# 7.7.2. Accountability

At randomisation, the trial treatment number will be provided and this reference will correspond to a trial treatment pack available in the local hospital pharmacy. The pharmacist will receive notification of the name and trial number of the randomised woman and will prepare the trial treatment pack for dispensing. The trial treatment packs will cover six treatment cycles for clomifene or letrozole and seven calendar months for metformin or placebo. A separate pack will contain 14 weeks supply of metformin or placebo to cover the time from conception up until 14 weeks of gestation for women that conceive while on the trial.

The local pharmacist should keep accurate records of trial drugs dispensed using a pharmacy log provided by the LOCI Trial Office. Trial drugs must be kept in the packaging supplied and under no circumstances used for other participants or non-participants.

**LOCI PROTOCOL** Sponsor's reference: RG\_18-272 v1.0 07-Nov-2019 Page 31 of 57 IRAS ID: 257918 EudraCT number: 2018-004641-16 ISRCTN: TBC

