4.2. Trial interventions

Letrozole for 5 days starting on day 2 or 3 of the menstrual cycle, plus metformin or placebo daily. Initial letrozole dose will be 2.5 mg daily and may be increased to a maximum dose of 7.5 mg daily until ovulation is confirmed, for a maximum of 6 treatment cycles. The comparison will be clomifene for 5 days starting on day 2 or 3 of the menstrual cycle, plus metformin or placebo daily. Initial clomifene dose will be 50 mg daily and may be increased to a maximum dose of 150 mg in a similar way to letrozole, for a maximum of 6 treatment cycles.

The trial supports and documents the local clinical prescription recommended for each participant. In addition, the use of a human chorionic gonadotrophin (hCG) trigger injection following ovulation induction will be permitted and appropriately documented for participants requiring it. The maximum dose of metformin will be 1500 mg daily and continued until 14 completed weeks of pregnancy or until the end of the 6 treatment cycles.

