9.10. Sensitivity and supportive analyses

Sensitivity analyses will be limited to the primary outcome and will consist of:

- Per-protocol analysis; this will comprise the adherent population as described in sections 5.4;
- No interaction of treatment effect (as a result of the two trial allocations) is assumed. To explore this assumption, a treatment group interaction parameter (randomisation 1 by randomisation 2) will be added to the base model for trial comparisons A and B only as comparisons C-E only include one of the randomisations[4.13]). A p-value for this interaction parameter will be produced and examined as well as the interaction coefficient and 95% CI. If this parameter is significant, then treatment effect estimates within randomisation 2 allocation (for randomisation 1) and randomisation 1 allocation (for randomisation 2) will be explored as per the subgroup analysis methods described in section 9.9. It should be acknowledged that any test for interaction will be underpowered to detect a significant effect.
- An analysis to assess the effect of missing responses for the primary outcome only. Unadjusted models will be utilised. This analysis will explore the possibility that missing

responses are 'missing not at random' (MNAR) using a tipping point approach. In this analysis, for women with missing outcome data, events will be added sequentially in each of the groups in turn to determine the point where the general conclusion changes (for example from positive to inconclusive in terms of the CI). An assessment can then be made about whether the event rate in the missing responses between groups is likely to be plausible when compared with the event rate in the non-missing data. Two scenarios will be considered as follows:

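### The per-protocol set for metformin/placebo depends on a phase that only pregnant women have, so it is selected on a necessary step towards live birth

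*SAP*

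**What the plan says.** SAP 5.4 measures adherence by tablet count, or by the woman's own estimate where counting is not possible, and splits it at 75% of the randomised allocation (the lower category is "number that received <75% randomised allocation"). Letrozole/clomifene adherence is reported for the ovulation-induction (OI) phase. Metformin/placebo adherence is reported separately for the OI and pregnancy phases, with the added rule that "participants will need to be adherent in both phases to be considered adherent overall in any analysis".

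SAP 9.10 applies this definition: "Per-protocol analysis; this will comprise the adherent population as described in sections 5.4". The scope of that section is set by "Sensitivity analyses will be limited to the primary outcome and will consist of", so the outcome concerned is live birth at or beyond 34 weeks.

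The pregnancy phase exists only after conception. Protocol 7.1 states that "Visit 2 is only for participants who have become pregnant". On supplies to those who conceive, Protocol 7.7.2 says: "A separate pack will contain 14 weeks supply of metformin or placebo to cover the time from conception up until 14 weeks of gestation". SAP 4.2 has metformin/placebo "continued until 14 completed weeks of pregnancy or until the end of the 6 treatment cycles". Neither document says how a woman who never conceives is classified under the both-phases rule, or what the 75% refers to when a pregnancy ends before 14 weeks.

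**The concern.** Under SAP 9.5 the primary outcome counts women who conceived within the treatment window and went on to a live birth at or beyond 34 weeks. Conception is therefore a necessary step to the outcome, and the adherence rule treats women differently according to whether they have taken that step. The per-protocol population is formed partly by something the treatments are meant to change.

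This is the only adherence-based analysis of the primary outcome in SAP 9.10. If it disagrees with the intention-to-treat result, readers may take the difference as evidence about metformin taken as intended, when it could come from how the set was formed.

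**Working it through.** **Inputs from the documents**
- Metformin versus placebo: 39% versus 29%, 1,520 women with data, so 760 per arm (SAP 4.7).
- Live birth per conception, from the three-arm trial cited in Protocol 1.2.2: 47/62 = 0.758 on clomifene and 56/80 = 0.700 on clomifene plus metformin; pooled 103/142 = 0.725. These counts are all live births, not only those at or beyond 34 weeks.
- Discontinuation for gastrointestinal side effects, from the Dutch trial cited in the same section: 16% on metformin, 5% on placebo.

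**Assumptions**
- The null live birth rate is 34%, the midpoint of 39% and 29%.
- Adherence is 84% versus 95%, the complements of 16% and 5%. The source does not identify these as pregnancy-phase figures.
- Within pregnant and non-pregnant women, adherence is unrelated to outcome. OI-phase adherence is unrelated to conception, so it cancels within an arm and affects only numbers.

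**The plan's own figure.** Two-sided 5% test of two proportions, 760 per arm, 39% versus 29%: power 98.5%, as stated. The documents give no figure for the per-protocol analysis.

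Let L be the live birth rate, r live birth per conception, p = L/r the conception rate, and a pregnancy-phase adherence.

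**Reading 1, literal: both phases required of everyone.** Women who never conceive cannot qualify.
- Per-protocol rate = L·a/(p·a) = L/p = r.
- Both arms show 0.70 to 0.76, whatever L is. If metformin acts only through conception, RR goes from 0.39/0.29 = 1.34 to 1.00 and the difference from 10 points to 0.
- Numbers at r = 0.725, with 84% versus 95% in each phase: 760 × 0.538 × 0.84 × 0.84 ≈ 288 versus 760 × 0.400 × 0.95 × 0.95 ≈ 274. Over r = 0.70 to 0.758 the ranges are 276–299 and 262–284.
- The chance of a significant result is then 5%, the test's own error rate.
- Under a true null this reading also gives RR 1.00. Its harm is that it hides an effect.

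**Reading 2: pregnancy phase not applicable to women who never conceive.** Pregnant women must pass two tests, the others one.
- Per-protocol rate = L·a / (1 − p + p·a).
- Null, L = 0.34, r = 0.725, p = 0.469:
  - metformin: 0.2856/(0.531 + 0.394) = 30.9%
  - placebo: 0.3230/(0.531 + 0.446) = 33.1%
  - RR 0.93, difference −2.2 points. With 84% versus 95% in the OI phase as well, about 590 versus 705 women remain and a nominal 5% test rejects about 13% of the time.
- Same null with p = 0.50: 0.2856/0.920 = 31.0% versus 0.3230/0.975 = 33.1%, RR 0.94.
- Planned effect, r = 0.725: 0.3276/(0.462 + 0.452) = 35.8% versus 0.2755/(0.600 + 0.380) = 28.1%, RR 1.28 instead of 1.34.
- Equal adherence of 80% under the null: 30.0% in both arms, RR 1.00.
- A wider gap, 70% versus 95%, under the null: 27.7% versus 33.1%, RR 0.84, rejection about 54%. Nothing in the documents supports 70%; it shows sensitivity only.

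**OI-phase adherence only.** The rate is L in each arm, so RR is 1.34 under the planned effect and 1.00 under the null. With 84% versus 95%, about 638 versus 722 women remain (760 × 0.84 and 760 × 0.95), and power is about 97%.

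**The case against.** The literal reading may not be what the authors meant. Non-pregnant women are not given pregnancy-phase drug, so a rule about both phases can be taken to cover the phases a woman has. SAP 5.3 also already provides a pregnant-women analysis of the primary outcome, labelled supportive, which the literal per-protocol set would largely repeat. That is a fair argument for Reading 2, but the SAP does not say so, and Reading 2 still makes membership depend on pregnancy.

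It can also be said that the regimen runs to 14 weeks of pregnancy, so an OI-only set no longer reflects full adherence to it. That is true, and is a real cost of the change.

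The illustrative size rests on borrowed figures. Women who cannot tolerate metformin may already fail the OI phase, which would narrow the gap between arms in pregnancy. This also stands.

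Three stronger inferences are tempting but not supported:
- That the analysis must be biased even when treatment has no effect. The literal reading gives a null RR of 1.00. Reading 2 distorts the null ratio only if pregnancy-phase adherence differs by arm.
- That the set is selected on live birth itself. Selection is on pregnancy. Nor is it settled that successes are mainly what is lost: if 75% is counted against the full 14-week supply, early losses fail too, which removes non-events and pushes the rate up.
- That women who conceive early automatically fail the OI threshold because tablets are counted against the whole supply. The SAP does not make the supply the denominator, and SAP 9.4 refers to a drug compliance form completed per cycle.

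**Conclusion.** The point holds as a defect in one sensitivity analysis. Under either reading, the both-phases rule conditions the per-protocol set on conception. Read literally, it removes an effect that acts through conception (RR 1.34 to about 1.00). With the pregnancy phase waived for non-pregnant women, it could turn a true null into about 31% versus 33% (RR 0.93 to 0.94), given assumed adherence of 84% versus 95%, and leaves RR at 1.00 if adherence is equal. The Reading 1 result also assumes no effect on outcome after conception.

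The intention-to-treat primary analysis is untouched. Unequal tolerability matters most where metformin is compared with none (comparisons B, D and E). In comparison C both arms take metformin, so there is less reason to expect unequal adherence, but the literal reading would still hide a letrozole effect acting through conception. Comparison A is affected only if metformin/placebo adherence is also required there, which the SAP does not state. The wording should be changed before the analysis is run.

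**What to change.** In SAP 5.4 and 9.10:
- For the per-protocol analysis, define metformin/placebo adherence on the OI phase only, for all women: tablets taken divided by tablets due up to conception or the end of OI, with the 75% threshold kept.
- Delete the both-phases requirement.
- Report pregnancy-phase metformin/placebo adherence descriptively among pregnant women, and state the denominator used when a pregnancy ends before 14 weeks.
- State which drug's adherence defines the per-protocol set in each of comparisons A to E.

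The cost is SAP wording; SAP 5.4 already has OI-phase adherence reported separately. The downside is that women who stop metformin/placebo in early pregnancy remain in the per-protocol set. OI-phase adherence is still a post-randomisation variable, so ordinary per-protocol bias remains and the analysis should continue to be read as supportive.
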